#### 5.5. Placement and repositioning of the cerclage pessary containing sustained-release progesterone

Once the cervix length and positioning have been examined by transvaginal ultrasound, and any vaginal infection has been ruled out or treated, the progesterone pessary should be implanted by a professional qualified and trained for that purpose. For placement, the participant must be lying in supine position.

The removal of the pessary will be done by vaginal examination at week 36 6/7 or earlier, if there is any medical indication for induction of premature labor or elective cesarean section. The pessary will also be removed from participants in preterm birth labor not responding to treatment with tocolytics.

During controls or visits to emergency departments or medical offices, participants who report vaginal discharge should be examined by a physician to rule out infection by relevant testing (vaginal discharge smears for PCR), and deliver the appropriate treatment without the need to remove the pessary. This condition will be considered an adverse event.

In the event that the medicated cerclage pessary is spontaneously expelled it, will be repositioned within maximum 72 hours; if this does not occur, the patient will be withdrawn from the study but considered in the final statistical analysis under the intention-to-treat principle.

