## 5 PROCEDURES

### 5.1. Recruitment and Screening

Patients will participate voluntarily and under informed consent. Participant selection will be performed by screening the general population of pregnant women with single fetus monitored by the Hospital Healthcare Network, to investigate by serial transvaginal ultrasound performed between gestation weeks 16 (0/7) and 24 (0/7) those patients who have a cervical length between 10 mm and 25 mm, and/or women with a single fetus and cervical length  $\geq 10$  mm presenting one or more of the following risk factors: a) preterm birth prior to 35 (34 6/7) weeks of gestation; b) premature rupture of membranes prior to 35 (34 6/7) weeks of gestation.

Gestational age will be determined by the last menstruation date and will be confirmed by measurement of the craniocaudal length obtained in the first trimester ultrasound, or by measurement of the cephalic circumference in the second trimester ultrasound predominating the actual date of the last menstrual period (LMPad).

The selected volunteers will be examined and those with vaginal discharge will undergo clinical examination and/or bacteriological investigation and if confirmed for infection, this will be treated with the appropriate antibiotic. In these cases, insertion of the sustained-release progesterone cerclage pessary will be performed subsequent to the end of treatment although before 24 (0/1) weeks of gestation.

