### 7.2.3 Acceptability

7.2.3.1 Ease of insertion. Measured by means of a questionnaire.

7.2.3.2. Pain of the patient at the time of insertion and during use of the pessary. The VAS will be applied from 1 to 10 at Visit 1 (admission, where questions 1 to 3 will be answered) and at the final study visit (where questions 4 and onwards will be answered).

7.2.3.3. Request for early removal of the pessary. Date, gestational age and reason for the pessary removal request will be recorded in the data record file.

7.2.3.4. Spontaneous expulsion of the pessary: Date and gestational age at the time of expulsion of the pessary without replacement will be recorded in the data record file.

7.2.3.5. Changes in vaginal discharge. The participant will be questioned about the presence, quantity, and physical characteristics of the discharge at every control visit. The clinical signs and symptoms of the patient will also be recorded.

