### 7.2.4. Local safety

7.2.4.1. Pain, irritation, pruritus, infection occurring in the patient during treatment.

7.2.4.2. Major maternal complications attributable to the pessary such as chorioamnionitis, severe vaginal or cervical trauma.

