### 9.2. Statistical analysis

For quantitative variables, descriptive statistics will be used (mean, standard deviation, minimum, median, maximum, 95% CI, and number of observations), whereas for categorical variables, frequencies and percentages analyses will be carried out. Results will be tabulated by treatment arm and pooled. The different vaginal formulations and progesterone will be formally compared. Results on efficacy and safety will be studied for each group separately and pooled, if relevant.

The proportion of women reporting adverse events during treatment will be cross-compared between the different doses using the Fisher's exact test or the Chi-square test.

All statistical analyses will be performed using the statistical software SPSS (Version 12) or Epistat 4.0.

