- (iv) Expulsion of the Pessary (Yes/No, Final Visit). The date, gestational age of expulsion of the pessary without replacement will be recorded in the log.
- (v) Sensation upon the release of the pessary (Final visit). This question has the following categories: 1 = never, 2 = almost never, 3 = occasionally, 4 = frequently, 5 = always; and only one of them will be selected.
- (vi) Release of vaginal fluid (Final visit). This question has the following categories: 1 = never occurred, 2 = No changes, 3 = little increase, 4 = big increased 5 = change in color; and only one of them will be selected.
- (vii) Sexual intercourse with pessary (Final Visit). This question has the following categories: 1 = better, 2 = as always, 3 = with discomfort, 4 = with pain, 5 = no intercourse; and only one of them will be selected.
- (viii) Request for early withdrawal of the pessary (Yes/No, Final visit). The date, gestational age and reason of withdrawal from the pessary will be recorded in the log.
- (ix) Recommendation (Yes/No, Final Visit).

For all the above items except number (iii), the information will be summarized in the frequency and percentage tables according to the total number of subjects included in each treatment group and will be handled only for informatory purposes.

Changes in vaginal discharge

Clinical evaluation and/or bacteriological research will take place, infections will be treated with the appropriate antibiotic in case it is confirmed. For these cases, the insertion of a cerclage pessary with sustained-release of progesterone, will take place later at the end of the treatment, but before 24 (0/1) weeks of gestation. It will be monitored in each visit.

In each control, the participant will be asked about the presence, quantity and physical characteristics of the vaginal discharge. To discard presence or absence of infections, the subject will be asked about the need to do a smear of the vaginal discharge for PCR and the need for treatment. The information will be summarized in tables of frequencies and percentages based on the total number of subjects included in each treatment group per visit. A generalized CMH test will be used to assess whether changes in vaginal discharge were different in any of the groups through time.

Children Evaluation

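### Rules for smear-testing vaginal discharge on treatment conflict, and the explicit adverse-event rule is undefined and written only for pessary users, so infection and discharge may be ascertained unequally across arms

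*Protocol*

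**What the plan says.** Infection is a named local safety outcome. Protocol 7.2.4 lists "Pain, irritation, pruritus, infection occurring in the patient during treatment", with no restriction to an arm.

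Three places describe smear testing during treatment:

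- Protocol 5.5, on placing and repositioning the pessary: "participants who report vaginal discharge should be examined by a physician to rule out infection by relevant testing (vaginal discharge smears for PCR". It goes on to say that staff should "deliver the appropriate treatment without the need to remove the pessary. This condition will be considered an adverse event".
- SAP Table 1: the vaginal discharge row is marked at every visit. From Visit 2 to the Final Visit the mark carries footnote 3, which consists of the single word for a smear. The row is not limited by group.
- SAP 10, changes in vaginal discharge: "the subject will be asked about the need to do a smear of the vaginal discharge for PCR and the need for treatment".

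Protocol 5.1 has a separate rule for the period before treatment: "those with vaginal discharge will undergo clinical examination and/or bacteriological investigation". Protocol 7.2.3 adds questioning on treatment: "The participant will be questioned about the presence, quantity, and physical characteristics of the discharge at every control visit".

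On analysis, SAP 10 plans a generalized CMH test of changes in discharge across groups over time. SAP 11.1 tabulates adverse events by treatment group. Protocol 9.2 says "The proportion of women reporting adverse events during treatment will be cross-compared between the different doses".

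**The concern.** The three on-treatment descriptions would test different women. A complaint-driven rule tests those who report discharge. A scheduled smear tests everyone who attends and also finds infections without symptoms. A question about need tests whoever is judged to need it. The number of infections found depends on which rule a site follows.

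The only explicit instruction to test and then record an adverse event sits in the pessary section. Read literally, a reported discharge may count automatically as an adverse event for a pessary wearer. For a capsule user it counts only if it meets the general definition in Protocol 8, which requires a change that is both unfavourable and unexpected. A site that regards discharge as expected with vaginal capsules could leave it unrecorded.

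The trial is open-label, and Protocol 5.4.5 puts a sticker on the pregnancy card showing pessary or capsule, so staff deciding whether to test will know the arm. If pessary wearers are tested or labelled more often, their reported rates can exceed the capsule rates with no true difference.

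**Working it through.** **Comparing the texts.** The plan states no figure on this point, so the main check is a reading of the passages against each other.

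| Item | Where | What it provides | Limited to an arm? |
|---|---|---|---|
| Smear on reported discharge | Protocol 5.5 | Examination and PCR smear | Sits in the pessary section |
| Smear by visit | SAP Table 1, footnote 3 | Marked Visit 2 to Final | No |
| Smear by question about need | SAP 10 | Subject asked | No |
| Explicit adverse-event sentence | Protocol 5.5 | The condition is an adverse event | Sits in the pessary section |
| Infection as a safety outcome | Protocol 7.2.4 | Named outcome | No |
| General adverse-event definition | Protocol 8 | Any study product, related or not | No |
| Recording of adverse events | SAP 11.1 | All recorded; infection of special attention | No |
| Visit frequency | Protocol 5.4.3 | Same for the three groups | No |
| Discharge questioning | Protocol 7.2.3, SAP 10 | At each control visit | No |

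Two points follow.

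1. The testing triggers differ between passages. They are not assigned one to each arm.
2. The adverse-event sentence in 5.5 is the only item on recording that is tied to the pessary, and what it refers to is unclear. Sections 5.4.3 and 5.6 have no equivalent.

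**Illustration of size.** The documents give neither an infection rate nor a detection rate, so these inputs are assumed: the same true rate in every arm (20% or 30%), full capture in the pessary arms, and capsule capture c of 50%, 70%, 90% or 100% of that. Group sizes come from Protocol 9.1: 90 per group, hence 180 if the two pessary arms are pooled.

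The observed capsule rate is the true rate × c; for example 0.30 × 0.50 = 0.15 and 0.20 × 0.70 = 0.14. For counts x1 of n1 and x2 of n2, with p̄ = (x1 + x2)/(n1 + n2), the uncorrected chi-square is

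X² = (x1/n1 − x2/n2)² / [p̄(1 − p̄)(1/n1 + 1/n2)],

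significant above 3.84 (two-sided 0.05). The probability of a false significant result is the sum of the binomial probabilities of all (x1, x2) pairs that exceed this limit.

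| True rate | c | Observed pessary v capsule | 180 v 90 | 90 v 90 |
|---|---|---|---|---|
| 20% | 50% | 20% v 10% | 57% | 47% |
| 20% | 70% | 20% v 14% | 22% | 18% |
| 20% | 90% | 20% v 18% | 6% | 6% |
| 30% | 50% | 30% v 15% | 79% | 68% |
| 30% | 70% | 30% v 21% | 34% | 28% |
| 30% | 90% | 30% v 27% | 8% | 7% |
| either | 100% | equal | 5% | 5% |

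The result depends almost entirely on c, which nobody can read from the documents.

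**The case against.** The strongest reply is that the inconsistency lies between passages, not between arms. Where the SAP means the pessary groups only, it says so, as it does for cervical changes, acceptability and the pessary row of Table 1. The discharge row and the SAP 10 text carry no such limit. Section 5.6 deals with capsule adherence, so its silence on adverse events is unremarkable. This stands, and it rules out two stronger readings that a reader might infer:

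- That infection counts as an adverse event only for pessary users. Protocol 7.2.4, Protocol 8 and SAP 11.1 cover it in every arm.
- That infection and discharge cannot be compared fairly. If one of the SAP rules were applied uniformly, the comparison could be fair.

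It can also be said that the passages fit together: ask at every visit, and take a smear when indicated. A one-word footnote on a discharge row need not mean a mandatory smear for every woman, and SAP version 3.0 is described as the English version, so some wording may come from translation. That is a fair reading, and the point about infections without symptoms depends on rejecting it. But the text does not settle the matter. SAP 1 makes the protocol the final reference, and the protocol's only on-treatment testing rule is the one in the pessary section.

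Finally, the false-positive figures rest on chosen capture rates. No passage specifies a pooled 180 v 90 test of infection. The adverse-event test in Protocol 9.2 is worded as between doses and does not clearly include capsules, and SAP 11 specifies tables without a test. The CMH test in SAP 10 concerns discharge, for which the questioning is the same in all arms. All of this stands, so the figures can only be illustrative.

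What the reply does not remove is that equal questioning does not ensure equal testing or equal labelling, and that a rule to record all adverse events captures only the infections that are found.

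**Conclusion.** The point holds as a conflict in wording that carries a risk of ascertainment bias. The trigger for smear testing during treatment differs between Protocol 5.5, SAP Table 1 (if footnote 3 means a scheduled smear) and SAP 10. The explicit adverse-event sentence appears only in the pessary section and leaves open whether it means discharge or confirmed infection.

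Whether bias arises depends on how sites apply these passages, and its size cannot be estimated from the documents. Under the assumed rates, false significance ranges from about 18-68% (90 v 90) or 22-79% (180 v 90) at 50-70% relative capture, down to 6-8% at 90% and the nominal 5% at equal capture. Those ranges show that the matter could be important if capture differed widely and negligible if it did not.

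This concerns a secondary safety outcome in an exploratory phase II trial. It does not touch the primary endpoint, but it is worth correcting because the remedy is cheap.

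**What to change.** 1. Reconcile Protocol 5.5, SAP Table 1 with footnote 3, and SAP 10 into one detection rule for discharge and infection during treatment. The choice of rule is the sponsor's. Put it in Protocol 5.4.3, which already covers the three groups, and have the other places refer to it.
2. State in the same place whether discharge alone or only confirmed infection is recorded as an adverse event, identically in every arm. Confirmed infection remains an adverse event in all arms under Protocol 8 and SAP 11.1.
3. In SAP 11, report confirmed infection by arm with the number of women tested beside it, so that a difference in testing is visible.

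The cost is mainly protocol and SAP wording, plus a count of women tested in the infection table. Any change in the number of smears depends on the rule chosen; Table 1 does not exempt the capsule group from the discharge row as it stands.

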#### 5.6. Adherence and resuming the treatment in patients assigned to the group treated with vaginal progesterone capsules.

Use of capsules at least during 80% of the exposure time, and resuming the treatment not later than 72 hours after discontinuation for any cause will be considered an acceptable adherence to treatment. If adherence of a patient is below 80% or the treatment is interrupted for more than 72 hours, she will be withdrawn from the study but considered in the final statistical analysis.

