6. POPULATION DEFINITIONS

In order to meet the needs of the sub-groups of the Protocol, the following population sub-groups are defined:

Per Protocol (PP): It is defined as the subset of participants who meet the criteria of selection, who expressed their desire to participate in the study, who signed the informed consent form, that the drug has been administered to them and have completed all the visits required or till the termination of the pregnancy as per Protocol.

Intention to treat (ITT): It is defined as the subset of participants who meet the selection criteria, showing their desire to participate in the study, who signed the informed consent form, that the drug has been administered to them, who have at least completed the initial visit and at least one of the subsequent visits to the pessary referred to in the Protocol.

The main efficacy analysis will be carried out with a focus Per Protocol (PP), however it will also be carried out per Intention to Treat (ITT) all the analysis. Otherwise, the main safety analysis will be completed as ITT.

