9. TREATMENT COMPLIANCE

For Group A, at the start of each visit, it will be recorded the number of capsules dispensed at the previous visit and the number of capsules used, the treatment compliance will be estimated in percentage. The compliance should be between 80 and 120% for each patient.

For groups B and C, it will only be recorded if removal of the pessary was necessary. In this case the subject will be early terminated from the study and the reason for discontinuation will be recorded.

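### Treatment lapses and pessary removal are written as exit from the study, so the per-protocol set that leads the efficacy analysis can lose women whom the protocol says are analysed

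*Protocol*

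**What the plan says.** **Protocol**
- Section 5.5 gives 72 hours to reposition an expelled pessary; "if this does not occur, the patient will be withdrawn from the study but considered in the final statistical analysis", with intention-to-treat named as the basis.
- Section 5.6 covers capsules: if adherence is under 80%, or if "the treatment is interrupted for more than 72 hours, she will be withdrawn from the study but considered in the final statistical analysis".
- Section 5.7 covers pessaries removed on request or for an unresolved adverse event. These women are not replaced, their data are analysed on the intention-to-treat principle, and women off the product have standard follow-up.
- Section 5.4.5 closes a case only at 36 6/7 weeks or preterm birth. Section 5.8 takes the pregnancy outcome from the hospital file or the treating physician.

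**SAP**
- Section 9, on removal of a pessary in groups B and C: "In this case the subject will be early terminated from the study and the reason for discontinuation will be recorded".
- Section 6 requires PP women to "have completed all the visits required or till the termination of the pregnancy as per Protocol". The ITT set is limited to treated women "who have at least completed the initial visit and at least one of the subsequent visits".
- Section 6 then ranks the two sets: "The main efficacy analysis will be carried out with a focus Per Protocol (PP"). All analyses are also run on ITT.
- Section 5 leaves women with only a baseline visit out of the tables and figures and keeps them in the listings.
- Section 1 makes the protocol the final reference, and section 4 reports no changes to it.

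**The concern.** Stopping treatment and leaving the study are different things. A woman who stops treatment can still be seen and her birth recorded. A woman withdrawn from the study has no stated schedule of further visits. Sections 5.5, 5.6 and SAP 9 use the second form for what are lapses or changes in treatment.

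The protocol tries to repair this by saying the women are still analysed. The SAP does not carry that through: the set that leads the efficacy analysis is defined by completion, and completion is what these rules interrupt. The exclusions arise after randomisation, in an open-label trial where the arm is known when the decision is made, and they may be related to the risk of early delivery. At stake is whether the leading comparison of spontaneous preterm birth still compares the groups as randomised. Visit-based data after exit, such as cervical length, are also exposed.

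**Working it through.** **Step 1. Follow each event through both documents.**

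| Event | Consequence | Protocol: analysed? | SAP PP (leads) | SAP ITT (also run) |
|---|---|---|---|---|
| Expelled pessary not back within 72 h (5.5) | Withdrawn from the study | Yes, by intention-to-treat | Can fail if she exits before the pregnancy ends | Kept if one later visit |
| Capsules below 80%, or gap over 72 h (5.6) | Withdrawn from the study | Yes | As above | Kept if one later visit |
| Pessary removed (5.7, SAP 9) | Early terminated (SAP) | Yes, by intention-to-treat | As above | Kept if one later visit |
| Any exit before a later visit | As above | Yes | Generally fails | Not included; out of the tables under SAP 5 |

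Two details limit the reach. PP has no adherence threshold, so a woman is lost only through uncompleted visits or follow-up. The last row should be uncommon for capsule lapses, because "at the start of each visit, it will be recorded the number of capsules dispensed": a shortfall is normally found at a later visit, which already satisfies the ITT condition.

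**Step 2. Reproduce the plan's own allowance.** Protocol 9.1 plans 90 completers per group and up to 10% non-completion. 90 × 1.10 = 99 per group, as stated (90 / 0.90 would give 100). The implied non-completion is 99 − 90 = 9 per arm. This is a planning estimate from all causes; it does not bound the number of exits under these rules.

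**Step 3. Illustrate the possible shift.** The documents give no rates of capsule gaps, expulsion or removal, and no control event rate. The following are assumptions:
- control rate r = 20% (range 10% to 30%);
- pessary rate 40% lower among women kept (the protocol's 40%, read as a relative reduction, which it does not specify);
- m = 3 or 9 women excluded of 99 per arm;
- excluded women at k = 1 to 3 times their own arm's rate.

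All-randomised rate in an arm = [(99 − m) × r + m × k × r] / 99.

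With control 20%, pessary 12% and m = 9, the PP difference is 20.0 − 12.0 = 8.0 points. At k = 3 the control rate is (90 × 20 + 9 × 60)/99 = 23.64% and the pessary rate is (90 × 12 + 9 × 36)/99 = 14.18%.

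| k control, k pessary | All-randomised difference (points) |
|---|---|
| 1, 1 | 20.00 − 12.00 = 8.0 |
| 2, 2 | 21.82 − 13.09 = 8.7 |
| 3, 3 | 23.64 − 14.18 = 9.5 |
| 1, 3 | 20.00 − 14.18 = 5.8 |
| 3, 1 | 23.64 − 12.00 = 11.6 |

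With m = 3 the two extremes are 20.00 − 12.73 = 7.3 and 21.21 − 12.00 = 9.2. With m = 9 and a 10% control rate, a 4.0-point PP difference becomes 2.9 to 5.8. At a 30% control rate, 12.0 points becomes 8.7 to 17.5. The shift can go either way.

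**The case against.** The best defence is that the protocol, read as a whole, keeps these women. A case closes only at 36 6/7 weeks or preterm birth, the outcome comes from records, women off the product have standard follow-up, and the SAP defers to the protocol. A woman followed to the end of her pregnancy could then meet the PP definition. Every analysis is also run on ITT, the study calls itself exploratory, and adverse events are recorded to the last contact, which may be a telephone call after withdrawal (Protocol 8).

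Much of this stands, and it limits the harm. It does not remove the conflict. The follow-up sentence in 5.7 speaks of withdrawal from the product and leaves standard follow-up undefined. No text says that visits continue after withdrawal from the study. No SAP population definition restores these women to the leading analysis, and the ITT set is not all randomised women.

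The illustration is also open to challenge. With equal multiples in both arms the shift at a 20% control rate is only 0 to 1.5 points. The extremes need triple risk in one arm only, and nine exclusions per arm all arising from these rules. That is why it is offered as an illustration.

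A reader might go further and infer that SAP 9 strips primary events from the pessary arms, because 5.5 also says: "The pessary will also be removed from participants in preterm birth labor not responding to treatment with tocolytics". The documents do not support this. A delivery that follows is naturally the end of the pregnancy, 5.4.5 closes the case at preterm birth, and footnote 4 to SAP Table 1 collects tocolysis and delivery data at the final visit. Nor do the differing adherence rules show a bias between arms: a pessary has no capsule count, a capsule cannot be removed, and the 72-hour limit is common to both.

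**Conclusion.** The concern holds as a conflict between the documents and in the ranking of the analysis sets. The protocol withdraws women from the study and says they are analysed; the SAP leads with a set they can fail, and its fallback set omits those with no later visit. The leading efficacy result can therefore exclude women for post-randomisation reasons, against the protocol's stated principle.

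The consequence is moderate. An ITT result is produced beside each PP result, and the birth outcome should mostly be obtainable. The 5.8 to 11.6 range around an 8.0-point difference rests wholly on the assumed control rate, effect, exclusions and risk multiples. A reader might infer that the trial's result will be biased towards the pessary, or that these women's outcomes will be lost. Neither follows: the documents give no rates from which size or direction could be computed, and 5.8 supplies an outcome source. Confidence is medium, because whether a given woman fails PP depends on how sites apply the follow-up wording.

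**What to change.** 1. **Make the rules stop treatment only.** In 5.5, 5.6 and SAP 9, replace withdrawal or termination from the study with: *recorded as off study treatment or non-adherent; remains in the study for outcome follow-up to 36 6/7 weeks or delivery*. In 5.7, state that this applies after any pessary removal.
2. **Close the other exits.** State that ex-post exclusion (5.4.3), a decision not to continue (5.4.4) and treatment non-compliance as a listed discontinuation (SAP 7) end treatment only and do not remove a woman from the main analysis.
3. **Change the leading set.** In SAP 6, define the main efficacy analysis as all randomised women in their randomised arm, using the birth outcome from the sources in 5.8, with PP as a sensitivity analysis. In SAP 5, remove the exclusion of baseline-only women from the efficacy tables.

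Decisions to remove a pessary or stop treatment stay with the clinicians. A woman who withdraws consent to follow-up is reported as such.

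**Cost.** No new data source is needed. The leading estimate will include off-treatment time and may understate the on-treatment effect, which PP still shows. Non-adherent women would have some extra visits. As an illustration, if 27 women (297 − 270) each needed all seven later visits, that is 27 × 7 = 189 of 297 × 8 = 2,376 planned visits, or 8.0%. The protocol wording may need ethics committee approval as a substantial amendment (section 12).
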